3.3 Study procedures

Methods and approaches for objective 1: Water quality at the point of collection as well as at the point of consumption will be analyzed by field based methods using membrane filtration and the quantification of fecal indicators organisms such as E.coli and total coliforms. Water quality measurements will also include detection of free residual chlorine levels, turbidity, pH, conductivity, and nitrate.

Household information on WASH infrastructure, knowledge, attitude and practices will be gathered by a combination of qualitative (structured observations) and quantitative methods involving structured household interviews using tablets with digital questionnaires. Household survey questionnaires will include specific questions assessing KAP of WASH and health including household information, access to water, WASH know how, practice, attitude, self-efficacy, planning, behaviors, health status and risk awareness, social norms, perception of the water system, information on WASH promotion, market information, wealth index, and observation through interviewers.

Methods and approaches for objective 2: To determine the burden of water-borne diseases and the health impact of the interventions, the following indicators will be assessed by a combination of qualitative and quantitative methods:

- Diarrhea: baseline diarrhea incidence will be assessed by asking households about diarrhea
 prevalence during past 2 weeks prior to data collection. Households participating in the study
 will be requested to fill out a diary on diarrhea prevalence between baseline and of follow-up
 assessment.
- Intestinal parasitic infections: stool analysis will be done for determining the prevalence and type of intestinal parasites. Kato-Katz, formal-ether and wet mount methods will be used for soil-transmitted helminthes and intestinal protozoa respectively.

- Nutritional status: Anthropometric measurements for age will be used to account for normal growth and development of children. Children with z-scores for weight-for-height, weight-forage, and height-for-age <2 standard deviations of the median of the WHO reference population will be considered wasted, underweight and stunted respectively.
- Nutritional deficiency: Physical examination and clinical observation including dermatosis, pale conjunctiva etc. will be conducted by a trained health care professional. (food security will be assessed through questions in the interview)
- Hemoglobin (Hb) level will be measured to determine anemia prevalence using Hemocue device.
- Data will be collected from local health centers to identify the recorded prevalence of intestinal parasitic infections, and the prevalence of severe diarrhea of the children in surveyed households.

Data collection tools and techniques

5 qualified interviewers with a minimum schooling qualification of intermediate level and with experience in conducting household surveys will be recruited for data collection. Each interviewer will be accompanied by a data collection assistant. It is assumed that an interviewer-team of 2 people will cover 6 households per day; 5 interviewer teams of 2 people therefore will collect data from 30 households per day (household interviews, collection of water samples, collection of stool samples and measurement of health indicators such as anthropometry, hemoglobin). Time required to conduct the interview, collect samples and measure health data shall not exceed 1.5 hours per household per survey. The period allocated to collect data for one panel (baseline/ final survey) is 3 months.

One lab assistant and one health assistant will supervise stool, blood collection and physical examination. The stools will be collected in labeled plastic cups and will be preserved. The samples will be processed for testing at the hospital. Parasitological examination of the feces will be conducted according to operating procedures defined by WHO. Random reprocessing of 5% of the stool samples will be performed for accuracy purpose. Presence of any parasitic infection will be defined by positive laboratory results for intestinal parasites. All the surveyed children with parasitic infections will be treated. Pre-testing of the data collection tools will be done and the instruments will be pilot tested in the area similar to the project area.

Timeline

		2018									2019												2020					
Activities	1	2	3	4	5	6	7	8	9	10	11	12	1	2	3	4	5	6	7	8	9	10	11	12	1	2	3	4
Health Impact Study Nepal																												
Study preparation, development study tools																												
Baseline Data Collection																												
Intervention Helvetas																												
Data Collection																												
Data Analysis																												
Paper Preparation																												
Information Dissemination																												

Expected biases

We do not expect any biases

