Previous collaboration activities with Helvetas in the WARM-P project area revealed significant changes in the hygiene and sanitation condition after a WASH education campaign. Nevertheless, a significant degree of water recontamination between the point of collection and the point of consumption was observed. The proposed study aims at assessing the impact of such an effective training strategy at household level, if the training is combined with an improved water quality intervention.

The impact study will be implemented in Western Nepal in collaboration with Helvetas International Cooperation in the context of their activities on Water Safety Planning in water supply schemes. The evaluation will assess the impact of two interventions aiming at increasing water quality at the point of consumption.

The study is an observational study. Children's caretakers in participating households, will participate twice in a quantitative interview. Health data will be collected from one or two children of participating households. Children's health will be analyzed on the basis of the following indicators: diarrhoea incidence (questionnaire), parasite infection (collection and analysis of stool samples), anthropometric measurements, clinical examination and finger prick tests. The examination of children will be conducted by qualified and trained health personnel. Only households will be involved in the study that have provided written informed consent.

The process of data collection will not cause any health risks to participating humans and therefore can be categorized into Risk category A in accordance with HRO Art.7.

Participating households will not receive any direct compensation for participating in the survey. However, participants will be informed about the outcomes of the study and the results of their personal examination. Those found infected with parasites will be treated in accordance with their infection at recommended doses following standard treatment schemes of WHO.

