Areas A, B and C will receive household hygiene (HHH), the WARM-P WASH training intervention that aims at improving uptake and use of the following WASH infrastructure elements at household level: the construction of hand-washing stations, dish drying racks, latrines and waste management pits. These infrastructure improvements will be coupled with behavior change training to strengthen improved WASH knowledge, and facilitate consistent practice. Hygiene trainings will be provided during adult literacy classes for caregivers, at schools and during door to door visits. Households complying with the intervention will be provided with a sticker at the door that indicates that the 5 indicators: safe water, better sanitation, personal hygiene, kitchen management and solid waste management have been reached.

The establishment of supply chains for water treatment products will not be part of HHH.

In addition to household level interventions, Area A, B and C will also focus on elements of water safety planning related to the respective water supply scheme, such as system upgrades and regular monitoring visits, while paying attention to the criteria below:

- Area A will equip the water supply schemes with a chlorination system so that chlorinated water is provided at the point of collection.
- Area B will focus on providing access to high quality products for household water treatment (for example high quality ceramic water filters) and safe storage, including training on adequate product operation and maintenance
- Area C will only receive HHH, without providing access to chlorinated water and without providing access to products for water treatment at the household level
- Area D will be the control areas and will not receive any intervention.

The study will be implemented as a collaborative project between Eawag, the Swiss Federal Institute of Aquatic Science and Technology and the NGO, Helvetas Swiss Intercooperation Nepal, Eawag will be responsible for the study design, data collection, data analysis and reporting in accordance with the research design (Step 1 & Step 3). Helvetas Swiss Intercooperation will be responsible for the implementation of activities defined under Step 2.

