7.3 Confidentiality and coding

Project data will be handled with uttermost discretion and is only accessible to authorized personnel who require the data to fulfill their duties within the scope of the research project. On the CRFs and other project specific documents, participants are only identified by a unique participant number.

All personal data will be coded. Codes will be used for the labeling of water samples and stool samples and health data. Household's GPS data will be collected to identify households for the second panel of data collection. The participant identification list and GPS information will be stored by the principal investigator. Access to anonymized digital data will be restricted to researchers analyzing data by password protection. Back-ups of password protected files will be stored on external hard-drives.

Only anonymized data will be used for data analysis and to communicate study results.

Water quality & Stool samples will not identified by participant name but by a unique participant number. Samples will appropriately stored in a restricted area only accessible to authorized personnel. Samples and materials required for the analysis will be disinfected after the analysis and disposed.

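### The protocol expects no bias, yet diarrhoea is reported by caregivers who know whether they received a visible intervention, so reporting and observer bias should be acknowledged and limited

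*Protocol*

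**What the plan says.** Protocol 3.3 has a paragraph on expected biases that consists of one sentence: "We do not expect any biases".

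Other parts of the protocol bear on that sentence:

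- **How diarrhoea is measured.** Section 1 names a questionnaire as the source and says that caretakers "will participate twice in a quantitative interview". Section 3.3 adds that "baseline diarrhea incidence will be assessed by asking households about diarrhea" over the preceding two weeks, and that households "will be requested to fill out a diary on diarrhea prevalence between baseline and of follow-up".
- **What caregivers know.** Under 3.2 the interviewers explain the study's aims and methods to caregivers before consent.
- **What each area receives.** Under 2.3, Areas A, B and C get door-to-door training, handwashing stations, latrines and other hardware, with chlorination in A and water treatment products in B. "Households complying with the intervention will be provided with a sticker at the door". Area D gets nothing during the study; under 3.2 it is served only after the final data collection.
- **Who records.** Under 3.3 the same two-person teams interview, observe, take water and stool samples and measure the child. The interview also covers WASH promotion received.
- **Partial protections.** Under 2.3 one organisation collects the data and another delivers the intervention. Under 3.3 health-centre records are collected, for diarrhoea only where it is severe. Stool is processed at a hospital. Under 7.3, "Codes will be used for the labeling of water samples and stool samples and health data".

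No section mentions blinding of households, interviewers or laboratory staff.

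**The concern.** A caregiver who has been trained, equipped and perhaps given a sticker for compliance has reason to report less diarrhoea than a caregiver in an area that received nothing, even if the children are equally ill. An interviewer who can see the sticker and the handwashing station may also probe or record differently. Either mechanism lowers reported diarrhoea in Areas A to C relative to Area D without any change in health.

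Adjustment for baseline does not deal with this. A reporting shift caused by the training arises only after baseline, so it stays in the comparison of change between areas.

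A larger sample does not help either, because the shift is systematic and becomes easier to detect as numbers grow. A plan that expects no bias gives the reader no reason to treat a difference in reported diarrhoea with more caution than a difference in stool results.

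**Working it through.** **Step 1: the statement against the procedures.** Three conditions together make differential reporting a plausible expectation: the outcome is reported by the participant's carer, the carer knows the allocation, and the carer knows the purpose of the study. Sections 1, 3.2 and 3.3 establish the first and third. The second follows from 2.3, since the interventions are visible and the control has no sham. A fourth condition, that the recorder can see the allocation, follows from the observation tasks and the door sticker. That households and interviewers are unblinded is therefore an inference, but the procedures leave little room for anything else.

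**Step 2: an illustration of size.** The protocol has no figure to reproduce.

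Inputs from Protocol 4.1: 375 households per area, 7% drop-out and a threshold of p < 0.05. Hence n = 375 × 0.93 = 348.75, about 349 per area.

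Assumed inputs, not in the protocol: true two-week prevalence p at follow-up, equal in both areas; relative under-reporting u in one trained area; a two-sided test.

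The reported prevalence is p in control and q = p(1 − u) in the trained area. With m = (p + q)/2, the chance of a significant apparent reduction is

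Φ{ [(p − q) − 1.96 × SE0] / SE1 }, where SE0 = √[2m(1 − m)/n] and SE1 = √{[p(1 − p) + q(1 − q)]/n}.

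With u = 0 this gives Φ(−1.96) = 0.025, which is the right comparator, because only reductions are counted.

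*p = 15%, u = 20%:* q = 0.12, m = 0.135, SE0 = 0.02587, SE1 = 0.02584. (0.03 − 1.96 × 0.02587)/0.02584 = −0.80, so the chance is **0.21**.

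*p = 15%, u = 30%:* q = 0.105, m = 0.1275, SE0 = 0.02525, SE1 = 0.02519. (0.045 − 1.96 × 0.02525)/0.02519 = −0.18, so the chance is **0.43**.

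**Step 3: allowance for clustering.** Section 4.1 mentions design effects and a design-based chi-square test, but gives no value. With an assumed design effect of 2 the effective n is 349/2 = 174.5.

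- u = 20%: (0.03 − 1.96 × 0.03658)/0.03655 = −1.14, so **0.13**.
- u = 30%: (0.045 − 1.96 × 0.03571)/0.03563 = −0.70, so **0.24**.

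**Step 4: range over the assumed inputs** (one trained area against control, no true effect).

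| True prevalence | u = 10% | u = 20% | u = 30% |
|---|---|---|---|
| 10%, no clustering | 0.07 | 0.15 | 0.29 |
| 15%, no clustering | 0.08 | 0.21 | 0.43 |
| 20%, no clustering | 0.10 | 0.28 | 0.56 |
| 15%, design effect 2 | 0.06 | 0.13 | 0.24 |

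In every row the apparent prevalence ratio is 1 − u (0.9, 0.8 or 0.7), from reporting alone.

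**The case against.** The best case for the protocol runs as follows.

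*The protocol has safeguards.* This is partly right. Having different organisations collect the data and deliver the intervention reduces the wish to please the provider, and health-centre records do not rely on what a caregiver tells the survey. But respondents still know what they received, and the records cover severe diarrhoea only.

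*The sentence is an expectation, so it is not strictly a contradiction.* This is fair. It is better described as a position that the procedures do not support.

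*The figures are driven by assumptions.* This stands. Prevalence, under-reporting and design effect are all assumed, and the results move widely with them. The calculation uses two-week prevalence at follow-up, whereas the protocol states two-week recall only for baseline and a diary between surveys; the diary is not modelled.

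A reader might also infer more than the documents support:

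- **That diarrhoea is the trial's headline outcome.** Section 2.2 lists it beside intestinal parasites, the hypothesis in 2.1 names parasitic infections, and the indicators in 2.3 stress egg counts. No section puts diarrhoea first.
- **That the three trained areas pooled against control show a still larger error.** The plan specifies no such comparison, so no figure for it belongs here.
- **That stool and haemoglobin results share the problem.** They do not depend on what a caregiver chooses to report.
- **That the sample codes reveal the area.** Section 7.3 describes a unique participant number and does not say what it contains.

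**Conclusion.** The point holds for reported diarrhoea. A flat statement that no bias is expected is untenable when caregivers report the outcome, know the study's purpose and their own intervention, and are interviewed by a team that sees the infrastructure. The existing protections help only in part.

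Under the central assumptions (15% true prevalence, no real effect, 20% or 30% under-reporting in one area), a false finding of benefit occurs about 21% or 43% of the time if households are independent, and about 13% or 24% with a design effect of 2, against 2.5% nominally. These figures show how sensitive the comparison is. They do not predict the bias in this trial, and the documents do not show that under-reporting will occur or how large it will be.

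The point does not invalidate the trial, which also measures outcomes that do not rest on caregiver report. It concerns how far a difference in reported diarrhoea can be read as a health effect.

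**What to change.** Replace the sentence in 3.3 with text that does the following:

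1. States that reporting and observer bias are expected for diarrhoea, because caregivers and interviewers can see the intervention.
2. States that the health conclusion rests first on outcomes that do not depend on caregiver report: stool parasites, haemoglobin and anthropometry. Reported diarrhoea is interpreted only alongside these and the health-centre records of severe diarrhoea. E. coli at the point of consumption is supporting evidence on exposure; it is a water-quality measure under objective 1 and not a health outcome.
3. Requires that stool sample codes carry no area identifier and that samples are read in mixed order at the hospital, so that readers are masked to area.
4. Places diarrhoea recall before the modules on knowledge, attitude and practice, on WASH promotion and on observation.

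The limits should be stated too. Masked stool reading protects the stool outcome only; haemoglobin and anthropometry are measured by the visiting teams. Question order does not affect the diary and does not hide a sticker seen on arrival. Nothing here removes caregiver under-reporting.

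The cost is a few sentences, a check of the code format and a setting in the tablet questionnaire, with no extra staff, visits or households. The downside is that a difference in reported diarrhoea alone could not support the health claim.

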3.4 Withdrawal and discontinuation

In is expected that some household may drop-out during the course of the study either due to challenges with relocation of households or due to mobility. A slight oversampling will be done to compensate for the loss of households between baseline data collection and the second survey.

4 STATISTICS AND METHODOLOGY

4.1. Statistical analysis plan

Descriptive statistics will be calculated to describe the characteristics of the population and the status of WASH indicators. Frequencies and percentage will be computed for categorical variables while means and standard deviations will be calculated for continuous variables. Positive cases identified during health screening will allow estimating point prevalence. Pearson's chi squared and Fisher's exact test will be applied for finding the association with the prevalence of diarrhea, intestinal parasites (single, multiple), nutritional disorders and risk factors. Means will be compared by student's t test or ANOVA. Repeated measures multiple regressions will be used to find an association between binary or continuous outcomes and adjacent variables. Logistic regression analysis will be used to compare repeated binary health outcomes per child in multiple groups. Univariate association between two binary variables will be assessed through 2X2 tables. Categorical variables will be compared using design based chi-square analysis. In all analyses, a p- value (threshold of significance) <0.05 will be considered statistically significant.

Sample size and power calculations using G*Power 3.1 revealed a sample size of 350 households in each group to detect a small effect between 4 groups with a correlation of 0.1 among repeated measures with 80% power and a one-tailed alpha of 0.05 (Erdfelder *et al.* 1996). A sample size of 300 households will be required to detect a small to medium effect in Cohen's f2 at one-tailed alpha of 0.05 and a statistical power of 95% with multiple linear regression and 15 predictor variables (Faul et al., 2009).

We will sample 375 households per study area, which will have the advantage to better balance potential design effects. The same sampling plan will be used during the follow up study in both beneficiary and control areas. In addition, a drop-out rate of 7% is being considered.

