2.3 Project design

Research design

A randomized controlled trial (RCT) will be conducted in a rural area, following a cross-sectional baseline assessment on situational factors, water quality at the point of collection and point of use, WASH infrastructure, knowledge, attitude and practice as well as health indicators using standardized tools. The follow-up assessment will be conducted 1 year after the intervention (if funding is available a second follow-up assessment 2 years after the intervention might be implemented). One to one matching with the intervention area will be done for the selection of the control area.

The study will comprise of the following intervention schemes

	Baseline scenario	Intervention	Nr of households
Area A	PWS	HHH + S-CHL	375
Area B	PWS	HHH + HWTS	375
Area C	PWS	HHH	375
Area D (Control)	PWS	-	375

PWS is an area with the availability of a piped water supply scheme, that has not yet received the WARM-P training intervention

HHH: household hygiene intervention in accordance with the WARM-P training, but not establishing access to products for household water treatment

HWTS providing access to high quality products for household water treatment and safe storage, including training on adequate product operation and maintenance

S-CHL providing scheme-level chlorination

Conceptual Framework of the Study

The framework of the study is based on the assumption that improved access to safe drinking water together with adequate hygiene and sanitation conditions will improve children's health by reducing diarrhea incidence as well as the incidence of intestinal parasitic infections and therewith improve children's nutritional status.

The framework illustrates that to have a sustainable effect on children's health status a combination of WASH infrastructure improvement and education interventions should be

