3.2 Recruitment, screening and informed consent procedure

Prior to data collection and intervention activities, the selected communities and their leaders will be informed about the goal, purpose and methodology of the study during community meetings. Households in the study site will be selected in accordance with randomized sampling procedures.

An interviewer team of two people will visit the selected households, inform the caregivers of children about the goal, purpose and methodology of the study and hand out the informed consent forms (in Nepali) and request written agreement. If a person is unable to read and write, the information is read out to them and consent will be provided by fingerprints. Households will also be given the contact information of Helvetas-Nepal in case they have any questions about the study. Data will only be collected from agreeing households.

Children displaying signs of defense against participating in the study or against one of the health measurements will not be involved in the study.

Participating households will not receive any direct compensation for participating in the survey.

However, all households in the project areas will benefit from the study by improved management of the drinking water supply, by receiving training on improved hygiene, sanitation and household water treatment and by receiving a facilitated access to products required for water treatment. In control areas, the information on water treatment and access to respective products will be provided after final collection.

Participants will also be informed about the outcomes of the study and the results of their personal examination. Those found infected with parasites will be treated in accordance with their infection at recommended doses following standard treatment schemes of WHO. If signs of infection or anaemia are visible in any of the older children in the participating households, also these older children will be provided with treatment.

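### Arms are allocated by area or water scheme, but the sample size treats households as independent, and the stated allowance for design effects is the drop-out allowance counted a second time

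*Protocol*

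**What the plan says.** Protocol section 2.3 defines the arms as Areas A to D, with 375 households each. Delivery is collective. For chlorination, "Area A will equip the water supply schemes with a chlorination system so that chlorinated water is provided at the point of collection". Areas A to C also receive scheme upgrades and monitoring visits, and part of the hygiene training runs through schools and adult literacy classes. The comparator is chosen at area level too: "One to one matching with the intervention area will be done for the selection of the control area". The only randomness described for households concerns who is sampled, not which arm they are in: "Households in the study site will be selected in accordance with randomized sampling procedures" (section 3.2).

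On sample size, section 4.1 says: "Sample size and power calculations using G*Power 3.1 revealed a sample size of 350 households in each group". The calculation is for a small effect (no number given), four groups, a correlation of 0.1 among repeated measures, 80% power and a one-tailed alpha of 0.05. Section 4.1 then adds "We will sample 375 households per study area, which will have the advantage to better balance potential design effects", and separately considers 7% drop-out. Section 4.2 gives a base of 300 per area and attributes the rise to 375 to drop-out.

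On tests, section 4.1 says "Pearson's chi squared and Fisher's exact test will be applied for finding the association" between health outcomes and risk factors, and "Means will be compared by student's t test or ANOVA". It adds regressions for repeated outcomes per child, and one further sentence: "Categorical variables will be compared using design based chi-square analysis".

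**The concern.** Households on one scheme share a water source, a training programme and an arm, so their outcomes are likely to be correlated. Two consequences follow.

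- **Error rate.** A test that ignores this correlation uses a standard error that is too small. Ordinary variation between schemes can then pass for an intervention effect more often than 5% of the time.
- **Power.** 375 correlated households carry less information about an arm difference than 375 independent ones, so a calculation for independent households does not support the stated power.

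The 0.1 in the calculation does not help. It describes the same unit measured twice, not different households on the same scheme. The protocol gives no ICC, number of clusters, cluster size or design effect. The point does not depend on detail that a separate SAP might hold: section 4.1 makes a positive statement about design effects and names specific tests.

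**Working it through.** **1. The protocol's own figure.** The 350 per group could not be reproduced. Taking Cohen's f = 0.10 for a small effect (an assumption), four groups, two measurements, correlation 0.1 and alpha 0.05, the between-groups repeated-measures test needs 604 households in total, or 151 per group. The group-by-time interaction needs 495 in total (124 per group), and a one-way ANOVA 1095 in total (274 per group). All of these treat households as independent.

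**2. What the surplus covers** (350, 375 and 7% from section 4.1; 300 from section 4.2).

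- 375/350 = 1.071, and 350 x 1.07 = 374.5, so the step to 375 matches a 7% drop-out allowance.
- 375 x 0.93 = 348.75, and 348.75/350 = 0.996. Nothing remains for a design effect.
- From the base of 300: 375/300 = 1.25 before drop-out and 348.75/300 = 1.16 after it. Section 4.2 assigns that surplus to drop-out as well.

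**3. Effect of clustering.** Households per scheme (m) and ICC are not in the protocol. I assume m = 25 (15 schemes of 25 give 375 per arm) and show a range of ICCs.

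- Design effect: DE = 1 + (m - 1) x ICC = 1 + 24 x ICC.
- Effective n per arm: 348.75/DE.
- Error rate of a naive two-group test at nominal 5%: 2 x (1 - Phi(1.96/sqrt(DE))) two-sided, or 1 - Phi(1.645/sqrt(DE)) one-tailed.
- Power, reading (a), with 350 per group taken to give 80% one-tailed: Phi(2.487 x sqrt(348.75/350/DE) - 1.645), where 2.487 = 1.645 + 0.842.
- Power, reading (b), the between-groups repeated-measures F test with f = 0.10: noncentrality 0.01 x (4 x 348.75) x 2/1.1/DE, with 3 and 4 x (15 - 1) = 56 degrees of freedom, at alpha 0.05.

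| ICC (assumed) | DE | Effective n | Naive error, two-sided | Naive error, one-tailed | Power (a) | Power (b) |
|---|---|---|---|---|---|---|
| 0.01 | 1.24 | 281 | 7.8% | 7.0% | 72% | 97% |
| 0.05 | 2.20 | 159 | 18.6% | 13.4% | 51% | 79% |
| 0.10 | 3.40 | 103 | 29% | 18.6% | 38% | 59% |

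Worked line for ICC 0.05: DE = 1 + 24 x 0.05 = 2.20. Naive two-sided error: 1.96/sqrt(2.20) = 1.321, giving 18.6%. Power (a): 2.487 x sqrt(0.9964/2.20) = 1.674, and Phi(1.674 - 1.645) = 51%. Power (b): noncentrality 25.36/2.20 = 11.53, giving 79%.

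Both error columns are shown because the sample size is one-tailed, while the analysis threshold of p < 0.05 does not state sidedness.

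**4. One area per arm.** The design table in section 2.3 lists one area per arm, while the intervention text in the same section speaks of schemes and control areas in the plural. If each arm is a single cluster, there are no degrees of freedom between areas within arm. No valid test of arm then exists, so no power figure applies, whatever the number of households.

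**The case against.** **The trial may not be underpowered.** A reader might infer from reading (a) that power falls well below 80%. The protocol does not establish this. The effect size has no number, the 350 does not reproduce, and under reading (b) power stays near or above 80% up to an ICC of about 0.05. This objection stands. What can be said is that the stated power is unsupported.

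**The design-based chi-square.** A reader might call the text self-contradictory because it names Pearson and Fisher tests as well as a design-based test. That is too strong. The Pearson and Fisher sentence concerns association of outcomes with risk factors and does not mention arms, and the design-based sentence speaks of comparison. Many health outcomes (infection, stunting, wasting, anaemia) are categorical, so the naive error rates need not apply to them. It remains unclear which test governs arm comparisons, and means and regressions are not covered at all.

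**Baseline data.** Repeated-measures models can remove differences between schemes that are constant over time, so not every natural difference would be read as an effect. This stands in part. The relevant ICC is then that of change, which is also not given, and t tests or ANOVA at follow-up alone remain exposed.

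**The regressions might include scheme.** Their covariates are unspecified, so a scheme term is not excluded. It is not named either. An area term could not serve, because area is the arm.

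**Conclusion.** The point holds, and it should be corrected before sampling. Three parts rest on the protocol alone:

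- allocation is by area or scheme, while the calculation assumes independent households;
- the claim that 375 makes room for design effects is wrong as written, because the 7% drop-out uses up the whole surplus, and section 4.2 gives the surplus a different base and a single purpose, drop-out;
- no method for clustering is named for means or regressions.

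It follows that, for any positive ICC within schemes, arm comparisons made with these tests and no cluster term exceed 5% error.

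The size is conditional. The table in the working rests on an assumed 25 households per scheme and assumed ICCs, and its two power columns differ only in how the undefined small effect is read. Neither column should be quoted as the trial's power. If each arm proves to be one area, the difficulty is one of identification: arm and area cannot be told apart.

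**What to change.** In Protocol section 4.1:

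1. For all arm comparisons, replace ordinary Pearson, Fisher, t test and ANOVA by mixed-effects or GEE models with the water scheme as cluster, the child or household as repeated unit, the baseline value included, and a small-sample correction.
2. State the number of schemes per arm. Restate the power for the planned 375 per area with design effect 1 + (m - 1) x ICC and an ICC range, applying the 7% drop-out separately. Delete the claim that 375 balances design effects, and reconcile the base of 350 with the 300 in section 4.2.
3. Where an arm already contains several schemes, spread the 375 sampled households over all of them. Do not require new schemes: each would need upgrades and, in Area A, a chlorination system, and nothing in the protocol shows that more are available.

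The cost is analysis wording, probably a less favourable power figure, and some travel. No households are added. The change protects the error rate and makes the power statement honest, but it does not by itself restore 80% power: 15 schemes of 25 is the very layout that gives 51% at ICC 0.05 under reading (a). If an arm turns out to be a single cluster, the analysis change cannot repair it, and section 4.1 should say so.
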